#### 6.9.1.2 Drug and Alcohol Screen

At Part 1 Screening (Visit 1), the beginning of the Part 1 Open-Label Titration Period for Xyrem-naïve subjects (Visit 1.1), the start of the Stable-Dose Period for subjects previously on Xyrem (Visit 2), the end of the Double-Blind Treatment Period (Visit 4), and during the Open-Label Safety Period at Visits 5, 7, 9, 12, and 15 ([Appendix 1](#) and [Appendix 2](#)), an alcohol test and a panel of urinary drug screens will be performed. During Part 2, an alcohol test and a panel of urinary drug screens will be performed at Part 2 Screening, at Visit 18 (for re-enrollers only), at every 6-month visit (Visits 24, 30, and 36), and at Part 2 Study Termination/Part 2 Early Termination (Visit 42) ([Appendix 22](#), [Appendix 23](#), and [Appendix 24](#)). The panel of urinary drug screens will test for the following prohibited substances. (A positive amphetamine result will not exclude a subject who is taking prescribed amphetamines.)

- Amphetamine (not prescribed)
- Barbiturates
- Benzodiazepines
- Cannabinoids
- Cocaine
- Opiates

#### 6.9.1.3 Estimated Total Blood Volume Required by Study

Estimated blood volumes for subjects in Part 1 not participating in the PK evaluation are listed in [Table 3](#). The approximate total blood volume to be collected for study assessments in these subjects is 45.5 mL over a period of one year.

Xyrem® (sodium oxybate) oral solution  
Clinical Study Protocol: 13-005 Amendment 5

Jazz Pharmaceuticals

**Table 3 Estimated Blood Volumes for Assays in Part 1 – Non-PK Subjects**

	Screening (Day -30 to -1) a	End of Stable- Dose (Week 3 – Week 10)	End of Double- Blind (Week 5 – Week 12)	Termination (Part 1 Early Termination or Week 52)	Total
Clinical chemistry	7.5 mL	--	7.5 mL	7.5 mL	22.5 mL
TSH		--	--	--	
hCG		--	Included in Chemistry	--	
Girls <8 years old: LH, FSH, estradiol Boys <9 years old: LH, FSH, testosterone		--	--	Included in Chemistry	
Hematology	2 mL	--	2 mL	2 mL	6 mL
HLA DBQ1 602	3 mL	--	--	--	3 mL
GH, prolactin	--	3.5 mL	Included in Chemistry	Included in Chemistry	3.5 mL
IGF-1	--	3.5 mL	3.5 mL	3.5 mL	10.5 mL
Approximate total blood volume per subject	12.5 mL	7 mL	13 mL	13 mL	45.5 mL

a If needed, additional screening time may be granted with permission of the Medical Monitor.

Estimated blood volumes for subjects who are participating in the PK evaluation are listed in [Table 4](#). The approximate total blood volume to be collected for study assessments in these subjects is 88.2 mL over a period of one year.

Xyrem® (sodium oxybate) oral solution  
Clinical Study Protocol: 13-005 Amendment 5

Jazz Pharmaceuticals

**Table 4 Estimated Blood Volumes for Assays in Part 1 – PK Subjects**

	Screening (Day -30 to -1) a	PK Night 1 b	PK Night 2 b	End of Stable- Dose (Visit 3)	End of Double- Blind (Visit 4)	Termination (Part 1 Early Termination or Visit 15)	Total
Clinical chemistry	7.5 mL	--	--	--	7.5 mL	7.5 mL	22.5 mL
TSH		--	--	--	--	--	
hCG		--	--	--	Included in Chemistry	--	
Girls <8 years old: LH, FSH, estradiol Boys <9 years old: LH, FSH, testosterone		--	--	--	--	Included in Chemistry	
Hematology	2 mL	--	--	--	2 mL	2 mL	6 mL
HLA DBQ1 602	3 mL	--	--	--	--	--	3 mL
GH, prolactin	--	--	--	3.5 mL	Included in Chemistry	Included in Chemistry	3.5 mL
IGF-1	--	--	--	3.5 mL	3.5 mL	3.5 mL	10.5 mL
Coagulation (Screening)	2.7 mL	--	--	--	--	--	2.7 mL
Pharmacokinetic samples	--	7 × 2 mL	7 × 2 mL	--	--	--	28 mL
Volume for flushing indwelling catheter	--	6 × 1 mL	6 × 1 mL	--	--	--	12 mL
Approximate total blood volume per subject	15.2 mL	20 mL	20 mL	7 mL	13 mL	13 mL	88.2 mL

a If needed, additional screening time may be granted with permission of the Medical Monitor.

b PK Night 1 and PK Night 2 will occur while subjects are on a stable dose of Xyrem during the study.

For subjects who continue directly into Part 2 from Part 1, no additional blood samples will be collected for clinical laboratory assays. Estimated blood volumes for subjects who re-enroll in Part 2 are listed in Table 5. The approximate total blood volume to be collected for study assessments in these subjects will be 9.5 mL.

**Table 5 Estimated Blood Volumes for Assays in Part 2**

	Part 2 Screening Visit 17 (within 2 weeks before Visit 18) a
Clinical chemistry	7.5 mL
hCG	Included in Chemistry
Hematology	2 mL
Approximate total blood volume per subject	9.5 mL

a If needed, additional screening time may be granted with permission of the Medical Monitor.

Per the World Health Organization, the existing guidelines for blood sample volume limits (ranging from 1–5% of total blood volume within 24 hours and up to 10% of total blood volume over 8 weeks) are consistent with the limited evidence available on “minimal risk” to children (Howie 2011). EU Guidelines (2008) for pediatric clinical trials state that, per

Xyrem® (sodium oxybate) oral solution  
Clinical Study Protocol: 13-005 Amendment 5

Jazz Pharmaceuticals

individual, the trial-related blood loss (including any losses in the maneuver) should not exceed 3% of the total blood volume during a period of 4 weeks and should not exceed 1% at any single time. Specific guidelines may vary, but a commonly used guidance from Seattle Children's Hospital ([Appendix 4](#)) recommends no more than 2.5% of total blood volume in one blood draw and no more than 5% of the total blood volume in a 30-day period. To ensure that the total blood loss (including PK samples, samples for clinical labs, and any procedural losses) will not exceed the Seattle Children's Hospital's recommendation, EU Guidelines, or any particular investigational site IRB or Independent Ethics Committee (IEC) eligibility guidelines for pediatric blood draws relevant to that site, the following time periods should be maximized for subjects with low body weight participating in the PK evaluation to minimize the amount of blood drawn over 30 days: the Screening Period for subjects on Xyrem at study entry, and the time from Visit 4 to PK Night 1 and from PK Night 2 to Visit 15 for all subjects who participate in PK evaluations during the Open-Label Safety Period.

### 6.9.2 Sample Collection, Storage, and Shipping

A local topical anesthetic agent such as lidocaine/tetracaine (Synera) topical patch, or lidocaine/prilocaine cream (EMLA) may be applied 20-30 minutes or 60-120 minutes, respectively, prior to venipuncture or placement of an indwelling catheter per the site's usual procedures. If a numbing preparation will be used, the study staff will confirm that the subject is not allergic to the preparation prior to the application. Screening blood samples will be obtained by venipuncture. An indwelling catheter for obtaining blood samples for PK assessment will be placed in subjects participating in the PK evaluation on PK nights. If the catheter becomes non-functional (e.g., clogged or infiltrated), a second indwelling catheter may be placed; however, if the attempt to insert this second catheter fails, the PK blood sample collection for that night will be discontinued.

#### 6.9.2.1 Clinical Laboratory Test Samples

The laboratory will supply detailed instructions and all containers for blood and urine investigations. Blood and urine sample volumes will meet the laboratory's specifications. The actual time of blood collection for all samples will be recorded.

#### 6.9.2.2 Blood Samples for Pharmacokinetic Analyses

For subjects participating in the PK evaluation, blood samples (2 mL) to measure plasma sodium oxybate concentrations will be collected on two PK nights (PK Night 1 and PK Night 2) at 0 (pre-dose), 0.75, 1.5, 2.5, 4 (pre-2nd dose), 4.75, and 8 hours after the first dose. PK samples will be taken within  $\pm 5$  minutes of the specified time points. The actual time of blood collection for all samples will be recorded.

**Study Personnel on PK Nights:** A physician, either the Investigator or a Sub-investigator, must be on call and be readily available during PK nights. An individual skilled in pediatric venous catheter placement must be present on PK nights when blood samples will be collected and processed for PK evaluation.

To determine sodium oxybate concentrations, blood samples will be drawn according to the time points specified and dispensed into labeled sodium heparin tubes.

[figure not shown]
Xyrem® (sodium oxybate) oral solution  
Clinical Study Protocol: 13-005 Amendment 5

Jazz Pharmaceuticals

The blood samples will be collected and processed according to the PK lab manual provided to the sites, and the plasma samples will be shipped to the bioanalytical laboratory on dry ice as directed by the sponsor.

The bioanalysis will be performed by a central bioanalytical laboratory [REDACTED].

Plasma samples for sodium oxybate concentration determination will be shipped Monday through Wednesday via overnight carrier [REDACTED], on the appropriate amount of dry ice, to:

On the day of shipment, please notify [REDACTED] by email [REDACTED] of the pending shipment, including sample shipment tracking information and sample information manifest in Excel format.

## 6.10 Dispensing Study Drug

Subjects on Xyrem at study entry will continue dosing with their own supply of drug during the Part 1 Screening Period; however, appropriate study drug will be provided on the screening PSG night and will be administered by or under the supervision of qualified study site personnel. Study drug will be dispensed to Xyrem-naïve subjects at the beginning of the Part 1 Open-Label Titration Period (Visit 1.1) and to subjects on Xyrem at study entry at the start of the Stable-Dose Period (Visit 2). For subject who re-enroll in Part 2, study drug will be dispensed at Visit 18. Study drug will be dispensed at study visits, excluding phone visits, according to the schedules of events ([Appendix 1](#), [Appendix 2](#), [Appendix 22](#), [Appendix 23](#), and [Appendix 24](#)).

Study drug doses should be prepared with the dosing dispenser (syringe) that is supplied in the study drug kit (dosing instructions provided by Jazz Pharmaceuticals). Instructions for dose administration of the study drug will be provided to subjects/parent(s)/guardian(s) by the site personnel.

Flavorant will be provided if available for study drug preparation if flavored diluent is requested by the subject and deemed appropriate by the Investigator (excluding PSG and PK nights). Instructions for preparation of study drug with flavored diluent will be supplied if flavored diluent is to be used. Additional drug dispensing visits will be made as required by State or local regulations.

On all PSG and PK nights, study drug will be administered by or under the supervision of qualified study site personnel.

The Investigator or designated pharmacist will maintain accurate records for all study drug administered or dispensed.

Xyrem® (sodium oxybate) oral solution  
Clinical Study Protocol: 13-005 Amendment 5

Jazz Pharmaceuticals

## 6.11 Pharmacokinetic Assessments

The PK profile for two doses of Xyrem will be evaluated over an 8-hour period in a subset of subjects on two PK nights. The PK parameters for plasma sodium oxybate concentrations will include, but may not be limited to: the area under the plasma concentration time curve (AUC), maximum plasma drug concentration ( $C_{max}$ ), and time to maximum plasma drug concentration ( $T_{max}$ ), over the first 4-hour dosing interval. In addition, sodium oxybate concentrations at 4.75 hours (0.75 hours after the 2nd dose) and 8 hours (4 hours after the 2nd dose) will be measured to estimate peak and residual exposure associated with the second nighttime dose. Dose proportionality will be based on the ratio of AUC values for each subject. Pharmacokinetics will be summarized for the 7-11 and 12-17 year age groups, and a comparison to historical PK data in adults will also be made.

The blood sampling schedule and calculation of required number of patients needed to meet the objectives of this study were determined by Sponsor scientists with expertise in Clinical Pharmacology and Biostatistics.

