### 1.1.1 Clinical Experience

#### 1.1.1.1 Adult Studies

The effectiveness of Xyrem in treating the two main symptoms of narcolepsy—EDS and cataplexy—in adult subjects was demonstrated in three controlled clinical trials with 611 patients with narcolepsy (398 subjects treated with Xyrem). Adverse events seen with frequencies of ≥5% and twice the rate of placebo in Xyrem-treated patients were nausea (20.9%), dizziness (19.7%), vomiting (8.5%), enuresis (6.5%), and diarrhea (5%). Xyrem was also evaluated in one Phase 2 and two Phase 3 randomized, controlled clinical trials in patients with fibromyalgia; however, Xyrem is not approved for fibromyalgia. Results of those studies indicate a similar safety profile to that seen in clinical trials for narcolepsy

Xyrem® (sodium oxybate) oral solution  
Clinical Study Protocol: 13-005 Amendment 5

Jazz Pharmaceuticals

(Moldofsky et al. 2010, Russell et al. 2011, Spaeth et al. 2012, Spaeth et al. 2013). A study in patients with moderate to severe sleep apnea was conducted as a post marketing commitment (requirement). Xyrem treatment was not associated with an increase in apnea hypopnea index (AHI) but some clinically significant desaturations were observed (George et al. 2010).

The PK of Xyrem was extensively characterized in the clinical program that supported use of this drug for the indications of EDS and cataplexy in patients with narcolepsy. Xyrem is eliminated almost exclusively by metabolism through the Krebs cycle and does not inhibit CYP enzymes (Xyrem US PI 2016). Following oral administration, Xyrem is absorbed rapidly and consistently across the clinical dose range, with an absolute bioavailability of about 88%. The average peak concentrations ( $C_{max}$ ) following administration of each of two 2.25 g doses given under fasting conditions 4 hours apart were similar. The average time to peak plasma concentration ( $T_{max}$ ) ranged from 0.5 to 1.25 hours. Following oral administration, the plasma concentrations of sodium oxybate increased more than dose-proportionally, with blood levels increasing 3.7-fold as the total daily dose is doubled from 4.5 to 9 g.

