### 3.1.7 Open-Label PK Evaluation

At certain study sites during Part 1, eligible subjects will additionally participate in the PK evaluation. Subjects will be stratified to two age groups: 7-11 years of age and 12-17 years of age. Up to 18 subjects in each of the two age groups will be eligible to participate in the PK evaluation. Every effort will be made to ensure a minimum of 12 subjects in each age group complete the PK assessments. If the variability of PK data in children and adolescents is comparable to that of adults, a sample size of 12 completers in each age group is expected to provide adequate precision to characterize the PK of sodium oxybate in each age group. However, when sufficient data are obtained to characterize the PK profile with adequate precision during the study, as determined by the Data and Safety Monitoring Board, or when enrollment of 100 subjects in the study has been reached, enrollment in the PK evaluation will stop and existing data will be analyzed and reported.

[figure not shown]
Eligible subjects will spend two nights in the clinic for the PK evaluation (PK Nights 1 and 2). PK evaluation will occur at any time while subjects are on a stable dose of Xyrem. On PK Night 1, subjects will receive one half of their usual and current total nightly Xyrem dose (administered as two equally divided doses, given while in bed at bedtime and 4 hours later). Subjects will return to the clinic for PK Night 2 and will receive Xyrem at their stable, usual dose (administered as two equally divided doses, given while in bed at bedtime and

Xyrem® (sodium oxybate) oral solution  
Clinical Study Protocol: 13-005 Amendment 5

Jazz Pharmaceuticals

4 hours later). Each divided dose must match a printed gradation (line) on the dosing syringe; therefore, if a dose cannot be measured using the lines on the dosing syringe, the dose should be decreased to the next lower printed line on the dosing syringe. For example, if a subject is supposed to take a total dose of 4.25 g on a PK night, then the two equally divided doses would be 2.125 g each. There is no printed line for 2.125 g on the dosing syringe. The next lower line on the syringe would be 2 g (see Figure 4). The subject would then take the two equally divided doses of 2 g each, which would equal a total nightly dose of 4 g. The actual doses taken will be recorded on the CRF.

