On PK Night 1, subjects in the PK evaluation will receive one half of their usual (stable) total nightly Xyrem dose (administered as two equally divided doses, given at bedtime and 4 hours later while in bed). On PK Night 2, PK subjects will receive their usual nightly dose (administered as two equally divided doses, given at bedtime and 4 hours later while in bed). Subjects whose equally divided dose does not match a line on the dosing syringe will take the dose that matches the next lower printed line on the dosing syringe (see [Section 3.1.7](#)). Blood samples for PK assessment collected on these PK nights will allow assessment of dose proportionality within subjects.

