### 7.1.3 PK Nights 1 and 2 - Subjects Included in the PK Evaluation

Subjects on Xyrem who are willing to participate in the PK evaluation may participate while they are on a stable dose of Xyrem during the study:

- Ensure that coagulations test have been performed within 30 days prior to PK night 1
- Ensure that a light dinner was taken  $> 2$  hours prior to dosing. The light dinner should be the same or similar on both PK Nights. The light meal may be taken at the clinic or at home.
- Confirm parent(s)/guardian(s) contact information.
- Administer study drug:
  - PK Night 1: Administer  $\frac{1}{2}$  of the subject's usual nightly dose, in two equally divided doses 4 hours apart. (Access IVRS/IWRS.)
  - PK Night 2: Administer the subject's usual nightly dose, in two equally divided doses 4 hours apart. (Access IVRS/IWRS.)

Note: Subjects whose equally divided dose does not match a line on the dosing syringe will take the dose that matches the next lower printed line on the dosing syringe (see [Section 3.1.7](#)).

- Obtain blood samples for sodium oxybate concentrations at the times specified in the schedule of PK Night procedures ([Appendix 3](#)).
- Obtain vital signs at the times specified in the schedule of PK Night procedures ([Appendix 3](#)).
- Monitor SpO2 continuously by pulse oximetry from immediately before the first dose through 8 hours after the first dose, and record at the times specified in the schedule of PK Night procedures ([Appendix 3](#)). Take an additional measurement while the subject is awake and before release from the clinic.
- Perform a brief neurological exam before discharge on the morning after PK assessment.
- Provide breakfast if the subject prefers to eat at the clinic.
- Ensure that subjects of driving age who received study drug during the PK nights will not be driving themselves when leaving the clinic.

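### Dose proportionality rests on an AUC and Cmax ratio with no dose term, although rounding down to syringe lines can push the actual full-to-half dose ratio above 2

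*Protocol*

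**What the plan says.** Section 5.3 gives the purpose of the two PK nights: "Blood samples for PK assessment collected on these PK nights will allow assessment of dose proportionality within subjects". Night 1 uses half the usual nightly total and Night 2 the full total, each as two equal doses 4 hours apart.

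The measure is set out in Section 6.11: "Dose proportionality will be based on the ratio of AUC values for each subject". The synopsis repeats it. Section 9.7, and the statistical part of the synopsis, take the ratio of AUC and of Cmax with 90% confidence intervals.

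The dosing rule is in Section 3.1.7: "if a dose cannot be measured using the lines on the dosing syringe, the dose should be decreased to the next lower printed line". Its worked example starts from a planned 4.25 g night: "There is no printed line for 2.125 g on the dosing syringe. The next lower line on the syringe would be 2 g". Sections 5.3 and 7.1.3 and Appendix 3 repeat the rule; in the words of Section 7.1.3, such a subject "will take the dose that matches the next lower printed line on the dosing syringe". Section 3.1.7 also says: "The actual doses taken will be recorded on the CRF".

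Two other analyses come near dose. Section 9.7 allows a regression of concentration on mg/kg dose, only if warranted. Section 9.1 plans ANOVA on log-transformed PK parameters and names no dose term.

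**The concern.** An exposure ratio says something about proportionality only when it is set against the dose ratio that produced it. If every subject's dose ratio were exactly 2, the plain AUC ratio would be enough. The protocol's own rounding rule breaks that for some subjects, so the stated measure, followed literally, pools subjects with different dose ratios.

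Read as full against half dose, the measure errs towards a more than proportional rise. That is the departure reported in adults, where Section 1.1.1.1 describes more than proportional kinetics "with blood levels increasing 3.7-fold as the total daily dose is doubled from 4.5 to 9 g". Section 6.11 adds that "a comparison to historical PK data in adults will also be made". The adult figure belongs to an exact doubling, so a paediatric ratio is on the same footing only where the actual dose ratio is 2.

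At stake is part of Secondary Objective 2. No test or decision rule depends on it.

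**Working it through.** **Inputs.** Night 1 is half the usual total; each night is split into two equal doses; each divided dose is rounded down to a line (Section 3.1.7). Every divided dose in routine use must also match a line (Sections 3.1.2 and 5.3). Table 1 lists 4.5 g/night as an initiation ceiling and 7.5 g/night as a maximum. Reductions are in multiples of 0.5 g/night (text after Table 1).

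**Step 1: one case without any spacing assumption.** A usual total of 8.5 g/night is one 0.5 g reduction from 9 g. Taken equally, it is 4.25 g per dose, which must be a line. Night 1 is 4.25 g in total, 2.125 g per dose, given as 2 g. Dose ratio: 4.25 / 2 = 2.125. If the example's 4.25 g is instead the usual total, Night 2 gives 2 g per dose. Night 1 gives 1 g per dose on the grid derived in Step 2 (1.0625 g rounded down), a ratio of 2.00. The example alone therefore does not settle the matter. That second reading needs an unequal-dose regimen, because 2.125 g is not a line.

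More generally, a subject on two equal doses is already on a line on Night 2. Only the Night 1 dose can be rounded, and only down, so the ratio is at least 2 whatever the spacing.

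**Step 2: line spacing.** Assume even spacing from zero. There is a line at 2 g and none above it up to 2.125 g. If 4.5 g/night in two equal doses is measurable, 2.25 g is also a line, so the spacing is 0.25/k for a whole number k. Every k of 2 or more puts a line above 2 g and at or below 2.125 g, which the example excludes. Hence k = 1 and the spacing is 0.25 g. The protocol's example then reproduces: 2 × 2 g = 4 g.

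**Step 3: dose ratio by usual total.** With floor meaning rounding down to a whole number of lines:

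- full dose = 0.25 × floor((total/2)/0.25)
- half dose = 0.25 × floor((total/4)/0.25)
- R = full/half
- error under proportional kinetics = R/2 − 1

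| Usual total (g/night) | Full / half divided dose (g) | R | Error |
|---|---|---|---|
| whole grams, 2 to 9 | e.g. 3.00 / 1.50 | 2.00 | 0% |
| 2.5 | 1.25 / 0.50 | 2.50 | 25% |
| 3.5 | 1.75 / 0.75 | 2.33 | 16.7% |
| 4.5 | 2.25 / 1.00 | 2.25 | 12.5% |
| 5.5 | 2.75 / 1.25 | 2.20 | 10% |
| 6.5 | 3.25 / 1.50 | 2.17 | 8.3% |
| 7.5 | 3.75 / 1.75 | 2.14 | 7.1% |
| 8.5 | 4.25 / 2.00 | 2.125 | 6.3% |

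So 7 of the 15 half-gram levels from 2 to 9 g exceed 2 and none falls below it. This counts dose levels, not subjects.

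**Step 4: if children behaved like adults (assumption, power law).** Exponent b = log2(3.7) = 1.888, and the unadjusted ratio is R^b. At R = 2 it is 3.70. At 4.5 g it is 4.62 (+25%), at 7.5 g 4.21 (+14%), and at 8.5 g 4.15 (+12%).

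**Step 5: cohort effect.** The dose mix is not given. As an illustration under proportional kinetics, take 12 completers with k of them at 7.5 g and the rest at whole-gram totals. The geometric mean ratio is inflated by (2.1429/2)^(k/12) − 1, which is 0, 1.7, 3.5 and 7.1% for k = 0, 3, 6 and 12.

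**The case against.** The strongest reply is that the protocol only names the building block. It never says the ratio is compared with 2 and never calls it unadjusted. It has the actual doses recorded, and dose normalisation is ordinary detail for a statistical analysis plan, which was not available here. A plan that normalised by actual dose would not contradict Sections 6.11 or 9.7. That is fair and limits the weight of the point. It does not remove it: the protocol states the measure repeatedly and never ties it to the recorded doses. The conditional mg/kg regression concerns concentration and does not correct the ratio.

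Other points stand as limits:

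- The syringe figure is missing. With uneven lines the sizes would change, and for subjects on unequal regimens the direction could too.
- The half-gram grid is constructed. The 0.5 g rule governs reductions only, and Table 1 gives upper limits.
- The adult figure is for unspecified blood levels at a doubled daily dose, while the paediatric AUC and Cmax cover the first 4-hour interval. Step 4 is therefore illustrative.
- The adult comparison is not expressly one of dose ratios.
- Of Table 1's three maxima, 6 and 9 g are unaffected. An adult-like 3.7 is 85% above 2, which an error of this size would not hide.

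**Conclusion.** The concern holds as a minor one. Followed as written, the measure pools unequal dose ratios and overstates the rise in exposure for affected subjects. The upward direction is certain for subjects on equal divided doses, and holds for the others if the lines are evenly spaced. The sizes above rest on 0.25 g spacing. Over 4 to 9 g/night, an affected subject's ratio is 6.3 to 12.5% too high under proportional kinetics, and more if the adult power law applied. The average over the PK group could be nil and is unlikely to be large. The consequence is confined to a descriptive secondary estimate and its confidence interval, so changing the text is worthwhile but optional. Confidence is medium, because the syringe figure, the dose mix and any later analysis plan were not available.

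**What to change.** In Sections 6.11 and 9.7 and in the synopsis, state that dose proportionality is assessed within subjects from the actual first divided dose recorded for each PK night, by:

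- (a) the geometric mean ratio, Night 2 to Night 1, of dose-normalised AUC and Cmax with 90% confidence interval, reference value 1; and
- (b) a within-subject power model of log AUC and log Cmax on log actual dose, reporting the slope with 90% confidence interval, reference value 1.

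Part (b) is needed because normalisation removes the dose-ratio effect exactly only when kinetics are proportional. With exponent 1.888, the normalised ratio R^(b−1) is 1.85 at R = 2 and 2.05 at R = 2.25, whereas the slope is 1.888 at both.

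The cost is one statement in three places and a little extra analysis. The doses are already collected; dosing, rounding and sampling stay as they are. If the statistical analysis plan already normalises by actual dose, only the protocol wording needs aligning.
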